10. SAFETY MONITORING AND ADVERSE EVENTS

10.1 Definitions

10.1.1 Adverse Event

An adverse event (AE) is any untoward medical occurrence in a patient or a clinical trial subject administered a medicinal product. An AE does not necessarily have a causal relationship with the administered treatment. The term can include any of the following events that develop or increase in severity during the course of the study:

- Any sign, symptom, or physical examination finding that worsens in nature, severity, or frequency compared to Baseline, whether thought to be related or unrelated to the condition under study.
- Any clinically significant laboratory abnormality or laboratory abnormality that requires medication or hospitalization.
- All reactions associated with the use of the study treatment, including those occurring as a result of an overdose, abuse, withdrawal phenomena, sensitivity, or toxicity to the study treatment.
- Concurrent illness.
- Injury or accident.

A pre-existing condition is one that is present prior to or at the start of the study, and is to be reported as part of the subject's medical history. It should be reported as an AE only if the frequency, intensity, or the character of the condition worsens during study participation.

10.1.2 Adverse Reaction

An adverse reaction (AR) is any untoward and unintended response to a medicinal product related to any dose administered. The phrase "response to a medicinal product" means that a causal relationship between the medicinal product and the AR is at least a reasonable possibility (i.e., there are facts [evidence] or arguments to suggest a causal relationship).

The definition of an AR also covers medication errors and uses outside what is foreseen in the protocol, including misuse and abuse of the product.

10.1.3 Unexpected Adverse Event or Adverse Reaction

An Unexpected AE or Unexpected AR is an AE or AR, the nature or severity of which is not consistent with the reference safety information (RSI) for the product (e.g., Investigator's Brochure).

10.1.4 Serious Adverse Event or Serious Adverse Reaction

An AE or AR is considered "serious" if, in the view of either the Principal Investigator or the Sponsor, it results in any of the following outcomes:

- Death.
- Life-threatening AE (i.e., AE in which the subject is at risk of death at the time of the event; it does not refer to an event that hypothetically might have caused death if it were more severe).
- Inpatient hospitalization or prolongation of existing hospitalization.
- Persistent or significant incapacity or substantial disruption of ability to conduct normal life functions.
- Congenital anomaly/birth defect in the offspring of an exposed subject.
- Important medical event that may jeopardize the subject or may require an intervention to prevent one of the above characteristics/consequences (i.e., event may not result in death, be life-threatening, or require hospitalization, but based on appropriate medical judgment, it may jeopardize the subject and may require medical or surgical intervention to prevent one of the outcomes listed above; examples include allergic bronchospasm requiring intensive treatment in an emergency room or at home, blood dyscrasias or convulsions that do not result in inpatient hospitalization, and development of drug dependency or drug abuse).

With regard to results obtained from tests in laboratory animals or *in vitro* testing, whether or not conducted by Sponsor, a SAE includes any event suggesting significant risk to human subjects.

10.1.5 Suspected Unexpected Serious Adverse Reaction

A suspected unexpected serious adverse reaction (SUSAR) is any SAE that is assessed as both unexpected and, in the view of either the Principal Investigator or the Sponsor, as an AR.

10.2 Adverse Event Reporting Period

AEs will be monitored continuously during the study from the time that the subject has provided written informed consent through the subject's last day of study participation. Subjects will be queried and events will be assessed at each clinic visit. A treatment-emergent AE (TEAE) is any AE with an onset from any time from administration of the study treatment through the last study visit, whether or not it is considered causally related to the study treatment.

10.3 Recording of an Adverse Event

The Principal Investigator is responsible for evaluating all AEs, obtaining supporting documents, and determining that documentation of the event is adequate. He/she is responsible for determining the severity of the AE and its relationship to the investigational drug. The Principal Investigator may delegate these duties to sub-investigators but must assure that these sub-investigators are qualified to perform these duties under the supervision of the Principal Investigator.

All AEs will be recorded in the subject's CRF. The detailed description of the event will include appropriately graded severity of the AE and its relationship to the investigational product. Severity will be categorized by toxicity grade according to the Common Terminology Criteria for Adverse Events (CTCAE) Version 4.03.

AEs not listed in the Common Terminology Criteria for Adverse Events version 4.03 will be evaluated by using the following criteria:

- Grade 1, Mild: Symptoms cause no or minimal interference with usual social and functional activities.
- Grade 2, Moderate: Symptoms cause greater than minimal interference with usual social and functional activities.
- Grade 3, Severe: Symptoms cause inability to perform usual social and functional activities.
- Grade 4, Potentially Life-threatening: Symptoms cause inability to perform basic self-care functions OR medical or operative intervention indicated to prevent permanent impairment, persistent disability, or death.
- Grade 5: Outcome of AE is death.

The relationship of the AE to the investigational drug will be determined by the Principal Investigator. Any AE that does not meet the definition of a suspected AR will be categorized as Not Related.

Any Grade 3 and 4 clinical laboratory results that represents an increase in severity from Baseline will be reported as an AE if it is not associated with a diagnosis already reported on the CRF. A Grade 1 or 2 clinical laboratory abnormality should be reported as an AE only if it is considered clinically significant by the Principal Investigator.

In the event of death, the cause of death should be recorded as the AE and reported as a SAE. "Death" is not the AE; "death" is an outcome. The term "death" should be reported as an SAE only if the cause of death is not known and cannot be determined. If an autopsy is performed, a copy of the autopsy report should be obtained if possible. The Principal Investigator should make every effort to obtain and send death certificates and autopsy reports to Sponsor.

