The 3 components of SB-913 (ZFN1, ZFN2, and hIDS Donor) will each be added to 200 mL of diluent (refer to the Pharmacy Manual) and adjusted to 0.25% human serum albumin. Total infusion volumes will depend on a subject's cohort assignment and body weight (kg). IV infusions will be administered while the subject is in the hospital or acute care facility (refer to the Pharmacy Manual).

The subject will remain in the hospital or acute care facility for at least 24 hours after completion of SB-913 infusion for observation, and will be discharged when all AEs and vital signs (temperature, heart rate, respiratory rate, and blood pressure) are stable.

After being discharged from the hospital or acute care facility, study visits are scheduled on Day 7; Weeks 2, 4, 6, 8, 12, 16, 20, 24, 28, 32, 36, 40, 44, 48, and 52; and Months 15, 18, 21, 24, 27, 30, 33, and 36 (see Section 6 and Appendix 1).

Liver function tests (aspartate aminotransferase [AST], alanine aminotransferase [ALT], total and direct bilirubin, alkaline phosphatase, LDH, albumin, and total protein levels) will be conducted for evaluation of AAV mediated immunogenicity twice a week during the first 20 weeks after SB-913 infusion and may be conducted at home if the subject is remote. Blood samples for liver function tests will be drawn 2-4 days apart when possible, except for the first week when they will be drawn on the Day 1 and Day 7 visits. Liver function tests will subsequently be conducted at all study visits.

Previous studies with IV AAV8 FIX gene therapy have shown that liver transaminitis due to AAV immunogenicity occurs between 2 and 9 weeks after infusion and resulted in loss of FIX expression, and that rapid institution of prednisone can control this immunogenicity. If in spite of pretreatment with prednisone or equivalent corticosteroid in this study there is evidence of transaminitis, the dose of prednisone or equivalent corticosteroid will be increased on a case-by-case basis, and liver function will be assessed twice a week until normalization of liver enzymes, and then per protocol thereafter.

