11.2 Dose Escalation Rules

Within each cohort, treatment will be staggered so that each subsequent subject will not be infused until the preceding subject has been observed for at least 4 weeks.

Dose escalation to the next cohort will not occur until at least 4 weeks after the last subject in the preceding cohort has been dosed and the safety data from the prior cohort has been reviewed by the SMC and the SMC has agreed to dose escalate.

Dosing and dose escalation will be paused if a Grade 3 or higher AE occurs, or if two Grade 2 AEs occur within the same organ class and persist for more than 2 weeks with therapy, provided these AEs are not related to the primary MPS II disease or treatment of the MPS II disease. In such an event, the SMC will be convened to assess for potential dose-limiting toxicity (DLT) and to provide recommendations on whether to expand the cohort at the same dose level, to dose deescalate, or to continue the study as planned (refer to the Stopping Rules).

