APPENDIX 3: IMMUNOSUPPRESSION REGIMEN

Prednisone or equivalent corticosteroid regimen is commenced 2 days prior to Day 0 of SB-913 infusion and given once daily unless otherwise stated. Subject's liver function will be monitored twice a week while on prednisone or equivalent corticosteroid. Blood for liver panel shall be drawn 2-4 days apart when possible, except for the first week when it will be drawn on the Day 1 and Day 7 visits. Tapering of prednisone or equivalent corticosteroid will only proceed if ALT/AST activity levels are stable or declining (based on the 2 assessments of the preceding week).

If subjects develop increased ALT > 2 fold Baseline while on prednisone or equivalent corticosteroid or after stopping prednisone or equivalent corticosteroid, the prednisone or equivalent corticosteroid regimen may be adjusted or restarted at the Principal Investigator's discretion after consultation with the Medical Monitor. Twice a week liver panel testing should continue until the prednisone or equivalent corticosteroid course has been terminated.

An ACTH stimulation (cosyntropin) test will be performed prior to the first prednisone or equivalent corticosteroid dose and again during Week 20 or at the end of the scheduled taper to ensure that the adrenal cortical function has not been suppressed. Should prednisone or equivalent corticosteroid treatment be repeated due to increased transaminase activity, the ACTH stimulation test will be repeated at the end of taper at the Principal Investigator's discretion.

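### Protocol 10.3 drops the treated-abnormality route to an AE that 10.1.1 lists, so a Grade 1-2 transaminase rise given extra corticosteroid can go unrecorded

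*Protocol*

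**What the plan says.** **Definition.** Protocol 10.1.1 opens its list with "The term can include any of the following events that develop or increase in severity during the course of the study". The laboratory entry reads "Any clinically significant laboratory abnormality or laboratory abnormality that requires medication or hospitalization". That gives two alternatives, and neither carries a grade limit.

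**Recording.** Protocol 10.3 splits laboratory results by grade. For the higher grades, "Any Grade 3 and 4 clinical laboratory results that represents an increase in severity from Baseline will be reported as an AE", unless a diagnosis already on the CRF covers the result. For the lower grades, "A Grade 1 or 2 clinical laboratory abnormality should be reported as an AE only if it is considered clinically significant" by the Principal Investigator.

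**Expected treatment of a transaminase rise.** Protocol 12.2 names transaminitis first among the key anticipated risks. Section 3.5 says that if it occurs despite prophylaxis, "the dose of prednisone or equivalent corticosteroid will be increased on a case-by-case basis". Appendix 3 sets a threshold ("If subjects develop increased ALT > 2 fold Baseline while on prednisone or equivalent corticosteroid", or after stopping it) beyond which the regimen may be adjusted or restarted at the investigator's discretion after consulting the Medical Monitor. Neither place names a CTCAE grade or asks for an AE record.

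**Where AE records are counted.** The primary endpoint is TEAE incidence (Protocol 13.4; SAP 2.2.1), tabulated from AE records (SAP 7.2.5). The dosing pause in Protocol 11.2 applies to a Grade 3 or higher AE, or "if two Grade 2 AEs occur within the same organ class and persist for more than 2 weeks with therapy". Section 12.3 uses the same counts to convene the SMC.

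**The concern.** The two sections give different answers for one kind of event: a Grade 1 or 2 laboratory abnormality that is treated but that the investigator does not call clinically significant. It is within the AE definition, and the recording rule says not to report it.

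The mismatch bears on the toxicity that the protocol most expects, and on one for which it foresees added medication. Two sites with the same ALT course and the same steroid change could enter different data for the primary endpoint. Because the restriction in 10.3 can only remove events, any resulting bias in TEAE incidence is downward. With at most 32 subjects over roughly 12 to 15 sites (32/15 = 2.1 to 32/12 = 2.7 subjects per site), differences in recording habit could not be separated from differences between cohorts.

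The Grade 2 part of the pause and SMC rule concerns events that persist under therapy. Treated Grade 2 events are therefore the ones it needs to see, and 10.3 leaves their entry to a separate judgement of clinical significance.

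**Working it through.** **1. The plan's own figure.** Protocol 13.1: 8 cohorts × (2 + 2) subjects = 32, the stated maximum. No alpha, power or effect size is given, so no sample-size calculation applies.

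**2. The two rules side by side.**

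| Laboratory abnormality | AE under 10.1.1? | Reported under 10.3? |
|---|---|---|
| Grade 1-2, clinically significant | Yes | Yes |
| Grade 1-2, treated, not called clinically significant | Yes, by the medication route | No |
| Grade 1-2, neither | No, by the laboratory entry | No |
| Grade 3-4, worse than Baseline | Not graded in 10.1.1 | Yes, unless under a diagnosis already reported |

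Only the second row conflicts. Nothing in the available text says that a steroid-treated rise counts as clinically significant, or must be reported. The opening of Section 8 is not in the public text and could not be checked.

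**3. Can a rise that prompts steroid be Grade 1-2?** Exclusion criterion 8 removes subjects with ALT or AST above 2.0 × ULN. If Baseline ALT is also within that limit, the Appendix 3 threshold of 2 × Baseline is:

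| Baseline ALT (× ULN) | Threshold (× ULN) |
|---|---|
| 0.5 | 1.0 |
| 1.0 | 2.0 |
| 1.5 | 3.0 |
| 2.0 | 4.0 |

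The documents do not reproduce the CTCAE limits. For any Grade 3 limit above 4 × ULN (an assumption), the threshold lies below Grade 3 for every such subject, so treatment can begin while the rise is still under the Grade 1-2 rule.

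**4. Effect on incidence.** SAP 7.2.5 divides subjects with the event by subjects in the Safety Analysis Set, so one omitted subject changes a row by 100/n points:

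- n = 2: 100/2 = 50 points.
- n = 4: 100/4 = 25 points.
- n = 32: 100/32 = 3.1 points.

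This applies to the preferred term if the subject has no other recorded episode of it. The SOC row moves only if the subject has no other TEAE in that SOC, and the any-TEAE row only if the subject has no other TEAE at all.

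**5. Effect on the trigger.** Suppose k qualifying Grade 2 events occur and each is recorded independently with probability q. At least two must be recorded. For k = 2 the probability is q²; for k = 3 it is q³ + 3q²(1 − q).

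| q | k = 2 | k = 3 |
|---|---|---|
| 1.0 | 1.00 | 1.00 |
| 0.9 | 0.81 | 0.97 |
| 0.75 | 0.56 | 0.84 |
| 0.5 | 0.25 | 0.50 |
| 0 | 0 | 0 |

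The documents give no value for q. The table shows how the trigger depends on it and does not estimate under-recording.

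**The case against.** **The sections can be read together.** Section 10.3 also says that all AEs go into the CRF, so its last sentence may be meant only to screen out untreated low-grade noise. That may well be the intention, but the sentence makes clinical significance a necessary condition and has no exception for treated results.

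**The combination is unlikely.** An investigator would have to change corticosteroid because of a rise and still call it not clinically significant. Appendix 3 also brings in the Medical Monitor. This stands: omission is a possibility, and the documents contain no evidence that it has happened. The SAP's full source verification (4.1) helps less, since a site that follows 10.3 would have an eCRF consistent with its source.

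**Liver data are seen by other routes.** The SMC evaluates laboratory results at each cohort review (11.5) and may be convened at any time for excessive or unexpected toxicity (12.3). SAP 7.3 gives liver summaries by visit and figures for each subject. This also stands, and a reader should not infer that the SMC would be blind to transaminitis. The backstop is partial: cohort review may take place 4 weeks after the last infusion, while Section 3.5 cites onset at 2 to 9 weeks in earlier AAV work. Laboratory figures do not enter the TEAE tables or the AE-based trigger.

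**Stronger readings that the text does not support.**

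- That 10.1.1 makes every treated abnormality an AE. Its lead-in is permissive.
- That every ALT or AST value between the Appendix 3 threshold and Grade 3 is exposed. The threshold names ALT only, and only rises that are treated and not called clinically significant are affected.
- That Grade 1 omissions weaken the SMC trigger. Grade 1 events never count towards it.
- That holding a taper step is covered. Whether that amounts to requiring medication is not settled by 10.1.1.

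**Conclusion.** The inconsistency is real and should be corrected. It is confined to Grade 1-2 laboratory abnormalities that are treated but not called clinically significant; Grade 3-4 worsening is handled by 10.3 without that judgement.

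For the primary endpoint, the possible effect is a downward, site-dependent error in the liver-related rows: 50 points per subject in a cohort of 2 and 25 in a cohort of 4. It would be wrong to infer that overall TEAE incidence moves by as much, since any other TEAE in the same subject leaves that figure unchanged. For the dosing pause and SMC trigger, only Grade 2 events lasting more than 2 weeks with therapy are at issue.

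The conclusion rests on a literal reading of the restriction in 10.3, and on treating a corticosteroid increase or restart for raised transaminases as medication that the abnormality required. The trial is descriptive and no hypothesis test is affected.

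**What to change.** Reconcile the last sentence of Protocol 10.3 with 10.1.1: a Grade 1 or 2 laboratory abnormality is reported as an AE if the Principal Investigator considers it clinically significant, or if it requires medication or hospitalization. Carry the same wording into any CRF completion instructions.

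Add a data-management check that matches corticosteroid increases and restarts for raised transaminases against AE records. Protocol 7.2 already requires corticosteroid treatment to be entered on the concomitant medications page, so the check can also cover subjects already dosed.

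The cost is one amended sentence and a small reconciliation task. Reported liver-related TEAE incidence may rise slightly. The change concerns recording only and leaves every treatment rule as it is.

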10.4 Serious Adverse Event Reporting Period

All SAEs, whether or not unexpected or considered to be associated with the administration of study treatment, must be reported immediately to Sponsor or its designees, and must be submitted to Sponsor or its designees on an SAE Report form within 24 hours of the Principal Investigator's discovery of the event. Please refer to the study reference manual for SAE reporting guidelines and contacts.

The reporting period for all SAEs is from subject consenting through the last study visit.

The Principal Investigator is responsible for promptly notifying the IRB/IEC or equivalent in accordance with local regulations of all SAEs. The National Institutes of Health (NIH) requires that all investigators participating in gene transfer research to report all SUSARs. SUSARs will be reported to the appropriate regulatory authorities (FDA/MHRA or equivalent) according to the requirements for expedited safety reporting. Sangamo or its designee will assume the responsibility for reporting SUSARs to the FDA/MHRA or equivalent.

All "serious" events must be followed with appropriate medical management until resolved or stabilized.

10.5 Recording of a Serious Adverse Event

SAEs reported by telephone must be recorded on a written SAE Report Form provided by Sponsor or its designees. The SAE report form must be submitted to Sponsor or its designees within 24 hours.

The Medical Monitor will then advise the Principal Investigator regarding the nature of any further information or documentation that is required. Follow-up reports must be submitted within 24 hours from the time that the additional information becomes available.

10.6 SUSAR Reporting Obligations

Sponsor or its designee will submit SUSAR reports to appropriate regulatory authorities (including Competent Authorities in all Member States concerned), Ethics Committees, and Principal Investigators as per local laws and regulations. Fatal and life-threatening SUSARs will be submitted no later than 7-calendar days of first knowledge of the event and follow-up information submitted within an additional 8 days. All other SUSARs will be submitted within 15-calendar days of first knowledge of the event.

Principal Investigators are required to report any urgent safety matters to Sponsor or its designee within 24 hours. Sponsor or its designee will inform the regulatory authorities, ethics committees, and Principal Investigators of any events (e.g., change to the safety profile of the study treatment, major safety findings) that may occur during the clinical trial that do not fall within the definition of a SUSAR but may affect the safety of subjects participating in the clinical trials, as required, in accordance with applicable laws and regulations. The reporting period for urgent safety issues is the period from the signing of the ICF through the last study visit.

The Principal Investigator will notify the IRB/IEC or equivalent of SAEs and urgent safety matters, in accordance with IRB/IEC or equivalent requirements and local laws and regulations. A copy of this notification must be provided to Sponsor or its designee.

10.7 Pregnancy and Pregnancy of a Partner Reporting

Pregnancies or pregnancies of partners occurring during this study are to be reported on the Pregnancy Reporting Form. In general, it is expected that pregnancies are reported in the same timeframe as SAEs. Regardless of whether the subject has discontinued participation in the study, the course of all pregnancies and any AEs will be followed to partum at minimum.

